7.6.3 SAE reporting to Boehringer Ingelheim (BI)

Upon inclusion into a trial, the patient's condition is assessed (e.g. documentation of history / concomitant diagnoses and diseases), and relevant changes from baseline are noted subsequently.

All adverse events, serious and non-serious, occurring during the course of the clinical trial (i.e., from signing the informed consent onwards through 30 days following cessation of treatment) will be collected, documented by the investigator.

The investigator shall report all SAEs and non-serious AEs which are relevant to a reported SAEs and AESIs by fax using BI IIS SAE form (Appendix D) to BI Unique Entry Point as detailed below in accordance with the following timelines:

- within five (5) calendar days upon receipt of initial and follow-up SAEs containing at least one fatal or immediately life-threatening event;
- within ten (10) calendar days upon receipt of any other initial and follow-up SAEs.

Boehringer Ingelheim Pharmaceuticals, Inc [name] [contact]

AND

NCCN at [contact] or [contact]

For each adverse event, the investigator will provide the onset date, end date, intensity, treatment required, outcome, seriousness, and action taken with the investigational drug. The investigator will determine the relationship and expectedness with the investigational drug to all AEs as defined in the listed adverse event section of Boehringer Ingelheim's (BI's) Investigator Brochure for the Product.

The investigator does not need to actively monitor patients for adverse events once the clinical trial has ended. However, if the investigator becomes aware of an SAE(s) that occurred after the patient has completed the clinical trial (including any protocol specified follow-up period), it should be reported to BI if considered relevant by the investigator.

Protocol Version: 02/02/24 Page 30 of 57

7.7 Timeframe for Reporting Required Events

Adverse events will be tracked during study treatment and for 30 days following the last day of study treatment. For the purposes of this protocol, adverse events collected and documented on CRFs are grade 3, 4, or 5 adverse events.

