7.6 Reporting to Boehringer Ingelheim and NCCN

7.6.1 Definitions

Adverse event

An adverse event (AE) is defined as any untoward medical occurrence, including an exacerbation of a pre-existing condition, in a patient in a clinical investigation who received a pharmaceutical product. The event does not necessarily have to have a causal relationship with this treatment.

Serious adverse event

A serious adverse event (SAE) is defined as any AE which results in death, is immediately life-threatening, results in persistent or significant disability / incapacity, requires or prolongs patient hospitalisation, is a congenital anomaly / birth defect, or is to be deemed serious for any other reason if it is an important medical event when based upon appropriate medical judgement which may jeopardise the patient and may require medical or surgical intervention to prevent one of the other outcomes listed in the above definitions.

Patients may be hospitalised for administrative or social reasons during the trial (e.g. days on which infusion takes place, long distance from home to site...). These and other hospitalisations planned at the beginning of the trial do not need to be reported as an SAE.

Severity of adverse event

The severity of the AE should be judged based on the following:

The severity of adverse events should be classified and recorded according to the Common Terminology Criteria for Adverse Events (CTCAE) <add version> in the (e)CRF.

Causal relationship of adverse event

Medical judgment should be used to determine the relationship, considering all relevant factors, including pattern of reaction, temporal relationship, de-challenge or re-challenge, confounding factors such as concomitant medication, concomitant diseases and relevant history. Assessment of causal relationship must be recorded for each adverse event.

Causality will be reported as either "Yes" or "No".

Yes: There is a reasonable causal relationship between the investigational product administered and the AE.

Protocol Version: 02/02/24 Page 28 of 57

No: There is no reasonable causal relationship between the investigational product administered and the AE.

Worsening of the underlying disease or other pre-existing conditions

Worsening of the underlying disease or of other pre-existing conditions will be recorded as an AE in the CRF.

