Changes in vital signs, ECG, physical examination, and laboratory test results Changes in vital signs, ECG, physical examination and laboratory test results will be recorded as an AE in the CRF, if they are judged clinically relevant by the investigator.

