7.6.2 Adverse Events of Special Interests (AESI)

The following events are considered as protocol-specified events of special interests:

Any gastrointestinal- and non-gastrointestinal perforation, leakage, fistula formation, abscess

In such case the following additional information need to be collected, documented in the respective comment field of the CRF page and the respective narratives of the SAE. That has to be forwarded to Boehringer Ingelheim:

- Location of perforation, leakage, fistula, abscess
- Location/extent of abdominal tumor manifestations,
- Imaging & reports (CT, ultrasound, endoscopy, pathology, etc.)
- Prior surgery (location, wound healing complications)
- Concomitant diseases with GI involvement (e.g., M Crohn, vasculitis, tuberculosis, diverticulitis)
- Thromboembolic events (or predisposition)

Drug-induced liver injury is under constant surveillance by sponsors and regulators and is considered a protocol-specified adverse event of special interest (AESI). Timely detection, evaluation, and follow-up of laboratory alterations of selected liver laboratory parameters to distinguish an effect of the investigational drug from other causes are important for patient safety and for the medical and scientific interpretation of the finding.

The following are considered as protocol-specified AESI:

- An elevation of ALT and / or AST > 5x ULN without bilirubin elevation measured in the same blood draw sample
- An elevation of AST and/or ALT >2.5 fold ULN combined with an elevation of bilirubin to >1.5 fold ULN measured in the same blood draw sample

Protocol Version: 02/02/24 Page 29 of 57

Patients showing above laboratory abnormalities need to be followed up until the protocol specific retreatment criteria have been met and according to Appendix C of this clinical trial protocol.

Protocol-specified AESI are to be reported in an expedited manner similar to Serious Adverse Events, even if they do not meet any of the seriousness criteria.

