- an elevation of AST and/or ALT >2.5 fold ULN combined with an elevation of bilirubin to >1.5 fold ULN measured in the same blood draw sample.

These definitions are in line with the current dose reduction recommendations as outlined in all study protocols for BIBF 1120.

Patients showing these laboratory abnormalities need to be followed up until the protocol specific retreatment criteria have been met

For patients with elevated ALT/AST values at baseline special considerations apply, if they are eligible for inclusion into the trial, e.g. if liver metastasis are present and do not qualify as exclusion criterion. For those special cases the BI contact person should be involved.

Procedures

- 1. Protocol-specified significant events are to be reported in an expedited manner similar as Serious Adverse Events, even if they do not meet any of the seriousness criteria and documented in the eCRF
- 2. Replication of the following laboratory tests for confirmation within 48 hours:
 - AST, ALT,
 - bilirubin measurement (total and direct bilirubin)
 - Alkaline Phosphatase
 - Haptoglobin
 - Complete blood count and cell morphology
 - Reticulocyte count
 - CK
 - LDH

The results of these repeated laboratory tests must be documented on the eCRF /CRF forms and reported immediately via the SAE form to BI.

- 3. An evaluation of the patient within 48 hours with respect to but not limited to:
 - Abdominal ultrasound or clinically appropriate other imaging and investigations adequate to rule out biliary tract, pancreatic, intra- or extrahepatic pathology, e.g. bile duct stones, neoplasm, hepatic tumour involvement, biliary tract, pancreatic or intrahepatic pathology, vascular hepatic conditions such as portal vein thrombosis or right heart failure. These data need to be collected, documented in the respective field of the eCRF / CRF / additional documentation form, and the respective SAE form has to be updated and forwarded to BI

Protocol Version: 02/02/24 Page 51 of 57

- detailed history of current symptoms and concurrent diagnoses and medical history
- detailed history of concomitant drug use (including non-prescription medications, herbal and dietary supplement preparations and eg steroids as concomittant suppportive treatment), alcohol use, recreational drug use, and special diets detailed history of exposure to environmental chemical agents

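### Section 7.7 limits CRF adverse events to grades 3–5, while 7.6.1, 7.6.2 and Appendix C send specific events to the CRF with no grade floor

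*Combined protocol and SAP*

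**What the plan says.** Section 7.7 sets the only grade floor: "adverse events collected and documented on CRFs are grade 3, 4, or 5 adverse events". It makes no exception for serious events, adverse events of special interest (AESIs) or events that change dosing.

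Other text sends events to the same record without a floor:

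- Section 7.6.1, on worsening: "Worsening of the underlying disease or of other pre-existing conditions will be recorded as an AE in the CRF".
- Section 7.6.1, on changes in vital signs, ECG, physical examination and laboratory results: these "will be recorded as an AE in the CRF, if they are judged clinically relevant by the investigator".
- Section 7.6.2, for any perforation, leakage, fistula or abscess: details are to be "documented in the respective comment field of the CRF page".
- Appendix C, Procedures, item 1, for the defined liver events: expedited reporting "even if they do not meet any of the seriousness criteria and documented in the eCRF".

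Two further sentences are more general. Section 7.6.1 says that severity is to be "classified and recorded according to the Common Terminology Criteria for Adverse Events (CTCAE) <add version> in the (e)CRF". Section 7.6.3 has "All adverse events, serious and non-serious, occurring during the course of the clinical trial" collected and documented by the investigator, and adds: "For each adverse event, the investigator will provide the onset date, end date, intensity, treatment required, outcome, seriousness, and action taken". It does not name the CRF.

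Section 15.3 plans a descriptive summary of toxicity by grade and does not say which grades it covers. Section 13.0 lists a summary of toxicities across sites in the safety monitoring report. Section 11.0 has a Toxicity Form submitted continuously, with no grade limit stated.

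**The concern.** A site with a grade 1 or 2 event of a kind named in 7.6.1, 7.6.2 or Appendix C has two instructions that cannot both be met. One keeps the event off the CRF and the other puts it on. The protocol provides for secondary sites (7.4, 7.5, 16.0), so sites could resolve this differently and supply adverse event data that are not comparable.

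There is also a consequence of 7.7 taken alone. Some treatment changes in 6.1 and 6.4 are triggered at grade 2. Under 7.7 the event behind such a change need not be in the adverse event dataset. The 15.3 summary, and the safety monitoring summary if it is built from the same data, could then omit events that altered treatment. Section 1.1 stresses the need for tolerable therapy in this population, so the omission would touch something the trial cares about, although toxicity is not a listed endpoint.

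**Working it through.** The plan gives no figure to reproduce here. The check is a comparison of texts, a count, and an illustration of scale.

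**1. The rules side by side**

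| Place | Events | Names CRF/eCRF? | Grade floor? |
|---|---|---|---|
| 7.7 | all adverse events | yes | grade 3 |
| 7.6.1 | worsening of disease or other conditions | yes | none |
| 7.6.1 | clinically relevant laboratory, vital-sign, ECG, examination changes | yes | none |
| 7.6.2 | any perforation, leakage, fistula, abscess | yes | none |
| Appendix C | defined liver events, serious or not | yes | none |
| 7.6.3 | all adverse events | no | none |

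Rows 2 to 5 contradict row 1 for any such event below grade 3. Row 6 does not have to: all grades in source records with grades 3–5 on the CRF would satisfy both 7.6.3 and 7.7.

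**2. Can the liver events fall below grade 3?** Appendix C defines them in multiples of the upper limit of normal, for patients with normal AST/ALT at baseline, and says that its definitions agree with the dose-reduction recommendations. Section 6.4 has a row for AST/ALT grade 2 with bilirubin grade 1 or higher. The combined criterion in Appendix C (AST/ALT above 2.5-fold with bilirubin above 1.5-fold) therefore appears to correspond to grade 2. This is an inference, since one text uses multiples and the other uses grades.

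**3. Treatment changes that can be triggered at grade 2**

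- Section 6.1 has 6 interruption criteria: nausea ≥3; vomiting ≥2; diarrhea ≥2 for more than 3 days; AST/ALT ≥2 with bilirubin ≥1; AST/ALT ≥3; other drug-related non-hematological ≥3. Three can be met at grade 2 (vomiting, diarrhea, combined liver).
- Section 6.4, split at each alternative, has 7 reduction criteria: diarrhea ≥2 for more than 7 days; diarrhea ≥3; vomiting ≥2; nausea ≥3; AST/ALT 2 with bilirubin ≥1; AST/ALT ≥3; other ≥3. Three can be met at grade 2, and the section limits dose adjustment to drug-related events.
- Taking out the liver criterion, which appears to match an AESI, leaves 3 − 1 = 2 in each list: vomiting and prolonged diarrhea. No event-specific CRF rule covers these two, so under 7.7 they stay off.

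**4. Scale.** The phase II NSCLC trial described in 1.3.2 had drug-related diarrhoea in 47.9% and vomiting in 42.5%, with grades not split. In 20 patients that would be 20 × 0.479 = 9.6 and 20 × 0.425 = 8.5, all grades. The share with a grade 2 event that triggers a treatment change is unknown. For an assumed share q, the expected number is 20q and the chance of at least one is 1 − (1 − q)^20:

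| Assumed q | Expected of 20 | Chance of at least one |
|---|---|---|
| 5% | 1 | 64% |
| 10% | 2 | 88% |
| 20% | 4 | 99% |
| 30% | 6 | >99% |

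This shows only that the gap need not be empty. It is not an estimate.

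**The case against.** The best defence is that 7.7 is deliberate. It presents its rule as one made for this protocol, and a grade 3–5 CRF is a legitimate choice for a 20-patient descriptive pilot. On that view 7.6 describes reporting to the drug supplier, and its unfilled version placeholder shows template text. A practical site might also treat the specific rules in 7.6 as exceptions to 7.7.

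Much of this stands. A reader might infer that 7.6.3 flatly contradicts 7.7. It does not, because it never names the CRF, and its sentence on details for each event sits under a heading about SAE reporting. A reader might also infer that the protocol itself orders grade 2 vomiting and diarrhea onto the CRF. Only the general severity sentence in 7.6.1 points that way, and that sentence sets the grading scale rather than saying which events are entered. Their absence is a consequence of 7.7, not a proven contradiction.

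Nor is the information lost. AESIs go to the supplier in an expedited manner even when non-serious, and the Appendix D form records action taken with the drug. A Treatment Form is due every cycle, and source records exist under 7.6.3. The Toxicity Form states no grade limit, which neither supports nor overrides 7.7.

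The defence does not reach the four specific rules in 7.6.1, 7.6.2 and Appendix C. They name the CRF or eCRF and are current text, and nothing makes them exceptions to 7.7.

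**Conclusion.** The inconsistency is real and minor. One section sets a floor at grade 3 with no exception. Four specific recording rules in three places have no floor, and no precedence is stated. As written, 7.7 also lets two event types that can change treatment at grade 2 stay out of the adverse event dataset and hence out of the 15.3 summary. The effect on the safety monitoring summary assumes that it draws on the same data.

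The documents do not support the stronger conclusions that a grade 3–5 CRF is improper in itself, that safety reporting fails, or that a particular number of patients is affected. The gap is confined to the adverse event dataset and the summaries made from it. The primary endpoint, the sample size and the clinical rules are unaffected.

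**What to change.** Amend 7.7 to keep the grade 3–5 base and add, at any grade:

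- all AESIs in 7.6.2 and the Appendix C liver events;
- the worsening and clinically relevant changes named in 7.6.1;
- every adverse event that led to interruption, reduction or discontinuation of nintedanib.

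Align the 7.6.1 severity sentence with this and fill in its CTCAE version (7.1.1 names 4.0). State in 15.3 which grades and events the toxicity summary covers. Section 7.6.3 can stand, and no dose or management rule changes.

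The cost is some extra CRF entries for about 20 patients, taken from records that 7.6.3 already requires. If patients are already enrolled, some entries would be retrospective. No new visit or procedure is needed.

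Recording all grades on the CRF would also remove the conflict, but it costs clearly more. The seven drug-related event rates quoted in 1.3.2 for the phase II trial sum to 57.5 + 47.9 + 42.5 + 28.8 + 13.7 + 13.7 + 9.6 = 213.7%. If they applied here, that is 20 × 2.137 ≈ 43 first occurrences, before repeats and other events. Some would be grade 3 or higher and recorded anyway.

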8.0 PHARMACEUTICAL INFORMATION

8.1 Nintedanib (BIBF1120)

8.1.1 Nintedanib Description

Molecular formula: C₃₃H₃₉N₅O₇S

Molecular weight: 649.8

8.1.2 Clinical Pharmacology

Ten hours following the first intake of nintedanib, mean plasma levels of VEGF and bFGF showed a trend to increase in relation to the baseline level, which could be indicative of successful blockade of angiogenesis receptors.

8.1.3 Pharmacokinetics and Drug Metabolism

After oral administration, maximum plasma concentrations generally occurred between 2-4 hours after dose. Steady state was latest reached within one week of dosing. The pharmacokinetics of nintedanib can be considered time-independent.

Nintedanib is mainly metabolized by esterases.

The terminal half-life of nintedanib varied between 7 and 19 hours. The major route of elimination was via fecal/biliary excretion. The contribution of renal excretion to the total clearance was low. The overall recovery was considered complete within 4 days after single dosing.

8.1.4 Suppliers

Nintedanib will be provided by Boehringer Ingelheim.

8.1.5 Dosage Form and Preparation

Nintedanib is provided as soft gelatin capsules containing a suspension of milled active as the salt. It is available in two dose strengths corresponding to 100 mg and 150 mg.

Protocol Version: 02/02/24 Page 31 of 57

8.1.6 Storage and Stability

Store below 30°C. Protect from exposure to high humidity.

8.1.7 Administration

Patients should take nintedanib approximately 12 hours apart at around the same time every day after food intake. Capsules should not be opened and should be swallowed unchewed with approximately 8oz of water.

9.0 CORRELATIVE STUDIES

9.1 Specific Hypothesis

The genomic landscape of cancer is complex and evolves through the process of clonal evolution innately and in response to treatment. Unbiased exome and transcriptome sequencing performed on tumor samples at time of diagnosis in responders and non-responders will help us identify unique variations that confer susceptibility to nintedanib. Moreover, genomic analysis at time of progression after treatment with nintedanib (after response (CR/PR/SD) lasting for 6 months or longer) will provide some unique insights into mechanisms underlying acquired resistance.

9.2 Tumor Biopsy Specimens for Research

9.2.1 Collection of Specimens

If archival tissue samples are available and/or a biopsy is obtained for clinical purposes at the time of disease progression, WUSM may request a tissue samplefor research sequencing, including whole exome and transcriptome sequencing. The specimens will be collected in accordance with standard of care practice and will be taken to the Washington University Tissue Procurement core for processing and storage per institutional practice.

Protocol Version: 02/02/24 Page 32 of 57

10.0 STUDY CALENDAR

All visits have a window of \pm 3 days.

	Screening	Day 1 of Each Cycle	End of Every Cycle	End of Treatment
Informed consent	X	-		
H&P, ECOG PS	X	X		X
CBC ⁶	X	X		X
CMP^7	X	X		X
Coagulation panel ⁸	X			
Urinalysis ⁹	X			
Pregnancy test	X^1			
CT scan – chest and abdomen with contrast	X		X	
Nintedanib		X^2		
Fresh biopsy for research sequencing ³				X^4
Adverse events assessment	X	X X ⁵		

- 1. Women of childbearing potential only; serum or urine
- 2. Taken twice a day every day of each 28-day cycle. Starting with cycle 64 cycles will last 12 weeks.
- 3. If a biopsy is obtained for clinical purposes at the time of disease progression, a sample may be collected for research purposes
- 4. To be monitored for 28 days after end of treatment
- 5. One follow-up visit at 28 days after end of treatment, then routine follow-up as per standard of care, with data collection regarding progression and survival to take place for the study
- 6. CBC with differential includes: WBCs, RBCs, Hemoglobin, Hematocrit, MCV, MCH, MCHC, RDW-CV, Platelets, MPV, Absolute Neutrophils, Lymphocytes, Monocytes, Eosinophils, and Basophils
- 7. CMP includes: Sodium, Potassium, Carbon Dioxide, BUN, Glucose, Creatinine, Calcium, Chloride, Albumin, AST, ALT, Alkaline Phosphatase, Bilirubin, Plasma Protein and Anion Gap
- 8. CoAg panel includes PT, PTT, and INR
- 9. Urinalysis includes: Color, Clarity, Specific Gravity, pH, Protein, Glucose, Ketones, Bilirubin, Blood, Urobilinogen, Nitrites and Leukocyte Esterase

11.0 DATA SUBMISSION SCHEDULE

Case report forms with appropriate source documentation will be completed according to the schedule listed in this section.

Case Report Form	Submission Schedule
Original Consent Form	Prior to registration
On-Study Form Tumor Biopsy Form	Prior to starting treatment
Treatment Form	End of every cycle
Toxicity Form	Continuous

Protocol Version: 02/02/24 Page 33 of 57

Treatment Summary Form Tumor Biopsy Form	Completion of treatment
	Baseline, end of every even numbered cycles (after every cycle starting with cycle 64), and end of treatment
Follow-Up Form	As per routine care

Any queries generated by Washington University must be responded to within 28 days of receipt by the participating site. The Washington University research team will conduct a regular review of data status at all secondary sites, with appropriate corrective action to be requested as needed.

12.0 MEASUREMENT OF EFFECT

12.1 Antitumor Effect – Solid Tumors

For the purposes of this study, patients should be re-evaluated for response every 8 weeks. In addition to a baseline scan, confirmatory scans should also be obtained not less than 4 weeks following initial documentation of objective response.

Response and progression will be evaluated in this study using the new international criteria proposed by the revised Response Evaluation Criteria in Solid Tumors (RECIST) guideline (version 1.1).³² Changes in the largest diameter (unidimensional measurement) of the tumor lesions and the shortest diameter in the case of malignant lymph nodes are used in the RECIST criteria.

